7.2 NULL AND ALTERNATIVE HYPOTHESES

No formal hypothesis testing is planned for this trial.

7.3 PLANNED ANALYSES

For the determination of the MTD, only MTD-evaluable patients will be considered. For other analyses of efficacy and safety endpoints, all patients in the treated set (i.e., patients

treated with at least one dose of trial medication) will be included in the analysis. Any other analysis sets will be defined in the Trial Statistical Analysis Plan (TSAP).

No per protocol set will be used in the analysis. However, important protocol violations will be summarised with details specified in the TSAP.

7.3.1 Primary endpoint analyses

[figure not shown]
In order to identify the MTD of the trial, the number of patients with DLTs at each dose level during the MTD evaluation period (first three weeks for Schedule A and the first 4 weeks for Schedule B) must be presented. Patients who discontinue during the first treatment course for reasons other than a DLT will be excluded from the determination of the MTD.

In addition, the number of patients with DLTs that occurred during the entire treatment period will be summarised at each dose level. The BLRM will be rerun to re-evaluate the MTD and RP2D together with all relevant data collected during the study.

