3.3.4.1 Withdrawal from trial treatment

An individual patient is to be withdrawn from trial treatment if:

- The patient wants to withdraw from trial treatment, without the need to justify the decision.
- Has radiological (or clinical) documentation of progressive disease on the current treatment.
- The patient needs to take concomitant drugs that interfere with the investigational product or other trial medication.
- The patient can no longer be treated with trial medication for other medical reasons (such as surgery, AEs, other diseases, or pregnancy).
- The patient has repeatedly shown to be non-compliant with important trial procedures and, in the opinion of both the investigator and sponsor representative, is not willing or able to adhere to the trial requirements in the future.

Given the patient's agreement, the patient will undergo the procedures for early treatment discontinuation and follow up as outlined in the [Flow Chart](#) (FC) and [Section 6.2.3](#).

For all patients the reason for withdrawal from trial treatment (e.g. AEs) must be recorded in the CRF. These data will be included in the trial database and reported. Patients who withdraw from treatment prior to disease progression should be encouraged to return for full EOT and follow-up assessments as outlined in the [Flow Chart](#). In particular, a follow-up visit should be performed wherever possible to ensure all adverse events are adequately followed up.

During the MTD evaluation period, patients withdrawn for a reason other than having a DLT or patients who miss more than one visit will be replaced after discussion between the sponsor and the Investigator if the information that needed to be collected during that visit is not available and makes the patient non-evaluatable for the PK analyses or safety parameters (including evaluation for DLTs).

Patients who come off trial due to a DLT will not be replaced.

If a patient should become pregnant during the trial, the treatment with BI 905681 must immediately be stopped. The patient will be followed up until delivery or termination of pregnancy (see [Section 5.2.6.2](#) for information on pregnancy forms). The data of the patient will be collected and reported in the eCRF until the last patient's last visit and any events occurring thereafter will be reported in the BI drug safety database as described in [Section 5.2.6](#).

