## **6.3           SUBJECT SETS ANALYSED**

The following subject sets will be defined.

- **Screened Set (ScS):** includes all patients who have signed the informed consent form and will be used for patient disposition.

- **Treated Set (TS):** includes all patients who received at least one infusion of BI 905681. The TS is used for both efficacy and safety analyses, and for summary of demographics, baseline characteristics, disease history, and concomitant therapies.
- **MTD Evaluation Set (MTDS):** includes all patients in the TS who were not replaced for the MTD determination. The MTD Evaluation Set is used for the primary analyses of DLTs and MTD determination. The list of replaced patients will be provided by the Clinical trial leader before DBL and documented in the decision log (2).
- **PK Analysis Set (PKS):** The PK set includes all subjects in the TS who provide at least one observation for at least one PK endpoint without important protocol violations relevant to the evaluation of PK. The PKS is used for all pharmacokinetic analyses

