## **7.4 PRIMARY ENDPOINT(S)**

### **7.4.1 Primary analysis of the primary endpoint(s)**

In order to identify the MTD of the trial, the number of patients at each dose level that had DLT during the MTD evaluation period (first three weeks for Schedule A) will be presented, excluding patients who discontinue during the first treatment cycle for reasons other than a DLT.

The BLRM as described in Section 7.1 of the CTP will be analyzed using the number of patients at each dose that had DLTs during the MTD evaluation period among the patients in the MTD set. The prior defined in Table 7.1: 1 of the CTP will be used for the analysis. The resulting posterior distribution of the DLT rates of the doses tested during the trial will be summarized using their mean, SD, 2.5% quantile, median, and 97.5% quantile. Additionally, the posterior probabilities of the DLT rate lying in the intervals [0, 0.16) (underdosing), [0.16, 0.33) (target dosing), and [0.33, 1] (overdosing) will be computed and listed for each dose. The posterior probabilities of underdosing, target dosing, and overdosing of the tested dose levels will additionally be visualized in a bar diagram that further displays which of the dose levels satisfy the EWOC criterion.

In addition, the number of patients with DLTs that occurred during the entire treatment period will be summarized at each dose level.

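### Excluding patients by their reason for leaving Cycle 1 can drop an observed first-cycle DLT from the MTD determination and the SAP's DLT table, although other sections count it

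*Protocol*

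**What the plan says.** Three sets of rules bear on who counts towards the MTD.

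**Exclusion by reason for leaving.** Protocol 7.3.1: "Patients who discontinue during the first treatment course for reasons other than a DLT will be excluded from the determination of the MTD". SAP 7.4.1 presents the number of patients with DLTs per dose level, "excluding patients who discontinue during the first treatment cycle for reasons other than a DLT".

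**Exclusion by replacement.** Protocol 7.3 says "For the determination of the MTD, only MTD-evaluable patients will be considered" but does not define evaluable. SAP 6.3 does so through replacement: the MTD set "includes all patients in the TS who were not replaced for the MTD determination". Under protocol 3.3.4.1, "patients withdrawn for a reason other than having a DLT or patients who miss more than one visit will be replaced", after discussion between sponsor and investigator, if the missing information "makes the patient non-evaluatable for the PK analyses or safety parameters". The same section adds: "Patients who come off trial due to a DLT will not be replaced".

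**Which DLTs count.** Protocol 4.1.7 makes DLTs that start in the first cycle the ones needed for escalation decisions. Protocol 5.2 says DLTs observed in the MTD evaluation period are considered for MTD determination. SAP Table 6.1: 2 runs that period from the first administration to 21 days later and does not shorten it if treatment stops.

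None of these places says that a patient with an observed first-cycle DLT is always included.

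**The concern.** Leaving out a patient who stops early without a DLT is ordinary practice, because that patient's DLT outcome is incomplete. It is different when a DLT has been observed: the outcome is then known, and the reason for stopping treatment does not change it.

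The rule as written does not separate the two cases. Anyone it removes wrongly is a DLT case, so the error runs in one direction, towards a lower apparent DLT rate. At stake are the DLT table for the primary endpoint and, where the sentence in protocol 7.3.1 is applied to the model, the posterior DLT rates and the EWOC check. With cohorts of two or three patients, one DLT carries much weight.

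**Working it through.** **Step 1. Can the case arise under the plan's own schedule?** In Schedule A the only Cycle 1 infusion is on Day 1 (protocol Table 4.1.1: 1). Suppose the patient stops on Day 10 for progression. The EOT visit is due within 7 days of the decision, so by Day 10 + 7 = Day 17, and it includes safety laboratory tests and bone biomarkers (Schedule A flow chart). AE collection continues to the follow-up visit 42–49 days after the last dose. A β-CTX rise of more than two-fold is a DLT (4.1.7). Bone markers are scheduled on Day 1 of Cycle 1, Day 1 of Cycle 2 and at EOT, so this patient's first scheduled post-baseline value is the EOT sample, normally taken after the decision to stop. The case is therefore possible, and it concerns a toxicity that protocol 1.4 anticipates.

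**Step 2. How does each rule treat a DLT that starts on Day 17?**

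| Place | Result |
|---|---|
| Protocol 4.1.7 | Starts in first cycle: counts |
| Protocol 5.2 | Within first 3 weeks: counts |
| SAP Table 6.1: 2 | 17 < 21 days: within the period |
| Protocol 7.3.1 | Stopped for progression: excluded |
| SAP 7.4.1, DLT count | Excluded |
| SAP 6.3 / 7.4.1, BLRM | Included unless replaced for the MTD determination |

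The first three rows contradict the fourth and fifth. The last two rows show the SAP using different sets for the DLT table and for the model.

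**Step 3. Reproduce the protocol's model.** Inputs: logit(π_d) = log α + β·log(d/d*), with d* = 4.5 taken on the per-infusion dose scale; the three-component prior of Table 7.1: 1; and 3 patients per cohort (Appendix 10.3 gives 9 patients in the first three cohorts). The posterior is proportional to the prior times the product over doses of π_d^r·(1 − π_d)^(n−r), with r DLTs in n patients. P(overdose at d) is the posterior probability that π_d ≥ 0.33, and EWOC requires it to be below 0.25. I integrated on a grid instead of using Gibbs sampling.

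- Prior P(overdose) at 1, 2.5, 4.5, 6.5 and 8.5 mg/kg: 0.074, 0.117, 0.178, 0.247, 0.299. Table 7.1: 2 gives 0.072, 0.114, 0.177, 0.244, 0.295.
- Scenario 3 (1/3 at 4.5), current dose: 0.115, against 0.116 in Table 10.3:1.
- Scenario 7 (0/3 at 4.5), next dose 6.5: 0.053, against 0.057.

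**Step 4. Keep or drop the patient with the DLT** (0/3 at 1.0 and 0/3 at 2.5 mg/kg throughout).

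| Data at 4.5 mg/kg | P(overdose at 6.5) | EWOC at 6.5 |
|---|---|---|
| 1/3, patient kept | 0.284 | blocked |
| 0/2, patient excluded | 0.066 | allowed |
| 0/3, excluded and a DLT-free patient added | 0.053 | allowed |

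At the dose levels in SAP Table 6.1: 1, with d* still 4.5, 1/3 at 5.0 mg/kg gives P(overdose at 7.0) = 0.305, and 0/2 gives 0.068. The pattern is the same.

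**The case against.** The strongest reply is that the effect is narrow and partly covered elsewhere. Much of this stands.

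- **The SAP's model.** In SAP 7.4.1 the reason-for-leaving filter governs the DLT count, while the BLRM runs on the replacement-defined set. A followed patient with an observed DLT is evaluable for DLTs and need not be replaced. A reader might infer that the SAP's BLRM necessarily loses this patient; its wording does not say so. The step 4 figures apply if protocol 7.3.1 is carried into the model, or if the patient is also listed as replaced.
- **Missed PK visits.** A reader might also infer that a patient with a DLT who stays in the trial but misses Days 8 and 15 would be replaced for PK and lost. The documents do not support this. Replacement needs non-evaluability and a discussion, not just missed visits. Sampling through Day 4 would normally still give Cmax and AUC to the last measured time. SAP 6.3 removes only those replaced for the MTD determination.
- **Drug-related stopping.** An AE that prevents a start of Cycle 2 within 14 days is itself a DLT unless clearly due to malignancy or another cause, so stopping for such toxicity is mostly a DLT reason already.
- **Other safeguards.** Escalation runs use all available data (protocol 3.1), the SMC decides jointly, and DLTs over the whole treatment period are summarised separately.

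These points limit the impact. They do not reconcile 7.3.1 and the SAP 7.4.1 count with the sections that count the DLT.

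**Conclusion.** The inconsistency is real and should be corrected. It affects a patient who stops in Cycle 1 for a reason other than a DLT and then has a DLT within 21 days of the first dose. Protocol 7.3.1 removes that patient from the MTD determination, and SAP 7.4.1 removes the patient from the DLT count.

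The shift from 0.284 to 0.066 shows what one such patient could do in a cohort of three with no earlier DLTs; it does not estimate what happened. The documents give no frequency for the case and do not show that it occurred. SAP section 4 says the trial ends early without an MTD and that only Schedule A was investigated. What remains exposed is the DLT table, its agreement with the BLRM output, and any reading of the posterior and EWOC displays that follows 7.3.1. It would go too far to conclude that an escalation decision was wrong.

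**What to change.** 1. In protocol 7.3.1, SAP 6.3 and SAP 7.4.1, state that every treated patient with a DLT starting in the MTD evaluation period belongs to the MTD set, whatever the reason for or timing of discontinuation.
2. Limit exclusion to patients without a DLT whose DLT window was not fully observed.
3. Use that one set for both the DLT table and the BLRM in SAP 7.4.1.
4. As a clarification only, say in protocol 3.3.4.1 and SAP 6.3 that replacement for PK reasons alone adds a patient for PK and does not remove the original patient from the MTD set.

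The cost is wording in four sections and no new data. The DLT estimate may become slightly less favourable. If no such patient occurred, a short statement to that effect in the report settles the point for this trial's results.

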7.3.2 Secondary endpoint analyses

All secondary endpoints will be analysed descriptively.

Details on statistical inference for PK parameters, e.g., dose proportionality using C_{max} and AUC etc., and all other secondary endpoints analysis will be specified in the TSAP.

7.3.4 Safety analyses

Adverse events will be coded using the Medical Dictionary for Drug Regulatory Activities (MedDRA). Standard BI summary tables and listings will be produced. All adverse events with an onset between start of treatment and end of the residual effect period (REP), a period of 42 days after the last dose of trial medication, will be assigned to the on-treatment period for evaluation.

All treated patients will be included in the safety analysis. In general, safety analyses will be descriptive in nature and will be based on BI standards. No hypothesis testing is planned.

Statistical analysis and reporting of adverse events will concentrate on treatment-emergent adverse events, i.e. all adverse events occurring between start of treatment and end of the residual effect period. Adverse events that start before first drug intake and deteriorate under treatment will also be considered as 'treatment-emergent.'

Frequency, severity, and causal relationship of adverse events will be tabulated by system organ class and preferred term after coding according to the current version of MedDRA at the database lock.

Laboratory data will be analysed both quantitatively as well as qualitatively. The latter will be done via comparison of laboratory data to their reference ranges. Values outside the reference range as well as values defined as clinically relevant will be summarised. Treatment groups will be compared descriptively with regard to distribution parameters as well as with regard to frequency and percentage of patients with abnormal values or clinically relevant abnormal values.

Vital signs, physical examinations, or other safety-relevant data observed at Screening, baseline, during the course of the trial and at the end-of-trial evaluation will be assessed with regard to possible changes compared to findings before start of treatment.

7.3.5 Pharmacokinetic and pharmacodynamic analyses

Refer to [Appendix 10.1](#) for pharmacokinetic parameters to be calculated using non-compartmental analysis (NCA). The derivation of pharmacokinetic parameters is described in detail in the current BI and [REDACTED] SOPs.

All patients in the treated set who received at least one dose of BI 905681 and provided at least one valid serum concentration value will be included in the pharmacokinetic analysis. Patients who are considered as not evaluable will be listed with their individual serum concentrations and individual pharmacokinetic parameters, however, they will not be included in descriptive statistics for serum concentrations, pharmacokinetic parameters or other statistical assessment.

Every effort will be made to include all concentration data in an analysis. If not possible, a case to case decision is required whether the value should only be excluded from half-life estimation or the complete analysis.

If a concentration is only excluded from half-life determination, it will be used for all other calculations (e.g. descriptive statistics) and for graphical presentation. If a concentration value is excluded from all calculations, it will not be presented graphically or used for the calculation of descriptive statistics and parameter determination. However the excluded concentration itself will be listed in the clinical trial report associated with an appropriate flag.

Concentrations will be used for graphs and calculations in the format that is reported in the bioanalytical report. Noncompartmental pharmacokinetic analyses of the serum concentration-time data will be performed using a validated software program, e.g. Phoenix WinNonlin Version 5.2. Only concentrations within the validated concentration range will be used for the calculation of pharmacokinetic parameters. For pre-dose samples, the actual sampling time will be set to zero.

Serum concentrations will be plotted graphically versus time for all evaluable patients as

listed in the drug serum concentration-time tables. For the presentation of the mean profiles, the geometric and arithmetic mean and the planned blood sampling times will be used. If the actual sampling time deviates significantly from the planned time, the corresponding serum concentration will be excluded from the calculation of descriptive statistics.

The following descriptive statistics will be calculated for analyte concentrations: N, arithmetic mean, standard deviation, minimum, median, maximum, arithmetic coefficient of variation, geometric mean, and geometric coefficient of variation. For the PK parameters in addition to the previous descriptive statistics P10, Q1, Q3, and P90 will be also calculated. The data format for descriptive statistics of concentrations will be identical with the data format of the respective concentrations. The descriptive statistics of pharmacokinetic parameters will be calculated using the individual values with the number of decimal places as provided by the evaluation program. Then the individual values as well as the descriptive statistics will be reported with three significant digits in the clinical trial report.

[REDACTED]

[REDACTED]

[REDACTED]

[REDACTED]

[REDACTED]

[REDACTED]

[REDACTED]

7.4 INTERIM ANALYSES

No formal interim analysis is planned.

The sponsor will continuously monitor safety. The dose-escalation design dictates that the sponsor and the SMC perform regular safety evaluations. These evaluations will be unblinded to dose.

If considered necessary, as soon as the MTD is determined, an evaluation of the safety aspects will be performed. Results of this evaluation will be documented and archived. If applicable, such an analysis will be defined in more detail in the TSAP.

7.5 HANDLING OF MISSING DATA

No imputation will be performed on missing efficacy data. Missing baseline laboratory values will be imputed by the respective values from the Screening visit. No other imputations will be performed on missing data although every effort will be made to obtain complete information on all AEs, with particular emphasis on potential DLTs.

7.6 RANDOMISATION

No randomisation will be performed.

7.7 DETERMINATION OF SAMPLE SIZE

The actual number of patients will depend on the number of dose cohorts and the cohort sizes actually tested. Given the pre-specified possible dose levels and the number of patients per dose level, simulation studies show a range (refer to [Table 10.3:3](#)) of 3 to 51 patients is needed to assess five dose levels for Schedule A. Assuming Schedule B has a starting dose of 1.0 mg/kg/q2w, a similar range of patients is required to assess the dose levels. Taken into account the number of patients recruited into the “back-filled” cohorts, around 30 patients are needed for each schedule. In total, the estimated sample size for the dose escalation phase is around 60 patients.

The replacement of patients is described in [Section 3.3.4.1](#).

8. INFORMED CONSENT, TRIAL RECORDS, DATA PROTECTION, PUBLICATION POLICY, AND ADMINISTRATIVE STRUCTURE

The trial will be carried out in compliance with the protocol, the ethical principles laid down in the Declaration of Helsinki, in accordance with the ICH Harmonized Tripartite Guideline for Good Clinical Practice (GCP), relevant BI Standard Operating Procedures (SOPs), the EU regulation 536/2014 and other relevant regulations.

Standard medical care (prophylactic, diagnostic and therapeutic procedures) remains the responsibility of the treating physician of the patient.

The investigator will inform the sponsor immediately of any urgent safety measures taken to protect the trial patients against any immediate hazard, as well as of any serious breaches of the protocol or of ICH GCP.

The Boehringer Ingelheim transparency and publication policy can be found on the following web page: trials.boehringer-ingelheim.com. The rights of the investigator and of the sponsor with regard to publication of the results of this trial are described in the investigator contract. As a rule, no trial results should be published prior to finalization of the Clinical Trial Report.

The certificate of insurance cover is made available to the investigator and the patients, and is stored in the ISF.

8.1 TRIAL APPROVAL, PATIENT INFORMATION, INFORMED CONSENT

This trial will be initiated only after all required legal documentation has been reviewed and approved by the respective Institutional Review Board (IRB) / Independent Ethics Committee (IEC) and competent authority (CA) according to national and international regulations. The same applies for the implementation of changes introduced by amendments.

Prior to patient participation in the trial, written informed consent must be obtained from each patient (or the patient's legally accepted representative) according to ICH / GCP and to the regulatory and legal requirements of the participating country. Each signature must be personally dated by each signatory and the informed consent and any additional patient-information form retained by the investigator as part of the trial records. A signed copy of the informed consent and any additional patient information must be given to each patient or the patient's legally accepted representative.

The patient must be given sufficient time to consider participation in the trial. The investigator obtains written consent of the patient's own free will with the informed consent form after confirming that the patient understands the contents. The investigator must sign (or place a seal on) and date the informed consent form. If a trial collaborator has given a supplementary explanation, the trial collaborator also signs (or places a seal on) and dates the informed consent.

Re-consenting may become necessary when new relevant information becomes available and should be conducted according to the sponsor's instructions.

The consent and re-consenting process should be properly documented in the source documentation.

